## 3.7.5 Telephone Visits (T10-T12)

The timing of telephone Visits T10, T11, and T12 is relative to Visit 9. Visit T10 should occur 7 days (±2 days) from Visit 9, T11 is 14 days (±2 days) from Visit 9, and T12 is 31 days (±2 days) from Visit 9.

### At these visits:

- Record changes to concomitant medications
- Record any AEs
- Record hypoglycemic events
- Titrate mealtime, correction and basal insulin dosages
- Answer subjects' questions/concerns

### **3.7.6** Clinic Visit (V13)

This visit will be conducted at least 30 days (+7 days) after Visit 2.

The following procedures will be performed at Visit 13:

- Record changes to concomitant medications
- Record any AEs
- Record hypoglycemic events
- Collect and review glucose meter data

Download and de-identify of unblinded CGM reports and pump reports for Medtronic CGM and pumps (

Confidential Page 48 of 70

mannkind

Download and de-identify of unblinded CGM reports/data and pump reports/data for Dexcom CGM and t:connect for Tandem pumps (

Confidential Page 49 of 70

- )
- Place blinded Dexcom G6 Pro CGM sensors on all subjects
- Titrate mealtime, correction and basal insulin dosages
- Record current basal insulin dosages
- Provide subject with any needed supplies (e.g., glucose test strips, Afrezza cartridges)
- Instruct participants to log meal announcements and Afrezza doses in the final 10 days

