- Visits T3, T4, T5, T6, T7, T8 (Telephone): Between Visits 2 and 9 in the clinic, several telephone visits will be conducted. During these visits, the Investigator will titrate insulin dosages, ask about changes to concomitant medications, record any adverse events (AE) and hypoglycemic events, and answer any questions/concerns raised by the subject.
- Visit 9 (Clinic): This visit will be conducted at least 30 days (+7 days) after Visit 2. CGM reports and pump reports will be downloaded from V2 to V9 using Carelink for Medtronic CGM and pumps, CGM reports/data and pump reports/data will be downloaded from V2 to V9 using Clarity for Dexcom CGM and t:connect for Tandem pumps. The site will de-identify all reports and data. The Investigator will titrate insulin dosages. Basal insulin dosages will be documented.
- Visits T10, T11, T12 (Telephone): Between Visits 9 and 13 in the clinic, three telephone visits will be conducted. During these visits, the Investigator will titrate dosages and answer any questions/concerns raised by subjects.
- Visit 13 (Clinic): This visit will occur 8 to 10 days prior to Visit 14. CGM reports and pump reports will be downloaded from V9 to 30 days after V9 using Carelink for Medtronic CGM and pumps, CGM reports/data and pump reports/data will be downloaded from V9 to 30 days after V9 using Clarity for Dexcom CGM and t:connect for Tandem pumps. The site will de-identify all reports/data. The Investigator will place a Dexcom G6 Pro blinded sensor on subjects in all groups. The Investigator will titrate insulin dosages. Additionally, Afrezza + AID and Afrezza + Degludec groups will be asked to log meal announcements and Afrezza doses in the final 10 days.
- Visit 14 (Clinic): At least 90 days following Visit 2 (+ 7 days), subjects will return for HbA1c measurement and safety assessments, including a final FEV1 measurement. The Investigator will download the blinded CGM data (CSV file) from the prior sensor wear. Additionally, CGM reports and pump reports will be downloaded from 30 days before V14 to V14 and from V13 to V14 using Carelink for Medtronic CGM and pumps, CGM reports/data and pump reports/data will be downloaded from 30 days before V14 to V14 and from V13 to V14 using Clarity for Dexcom CGM and t:connect for Tandem pumps. The site will de-identify all reports and data. Basal insulin dosages will be documented.

Planned Sample Size:

25 subjects (10 in each Afrezza group, 5 in AID Control group)

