**Visit 13 (Clinic):** This visit will occur 8 to 10 days prior to Visit 14. CGM reports and pump reports will be downloaded from V9 to 30 days after V9 using Carelink for Medtronic CGM and pumps, CGM reports/data and pump reports/data will be downloaded from V9 to 30 days after V9 using Clarity for Dexcom CGM and t:connect for Tandem pumps (

Confidential Page 25 of 70

). The site will de-identify all reports/data. The Investigator will place a Dexcom G6 Pro blinded sensor on subjects in all groups. The Investigator will titrate insulin dosages. Additionally, Afrezza + AID and Afrezza + Degludec groups will be asked to log meal announcements and Afrezza doses in the final 10 days.

**Visit 14 (Clinic):** At least 90 days following Visit 2 (+ 7 days), subjects will return for HbA1c measurement and safety assessments, including a final FEV1 measurement. The Investigator will download the blinded CGM data (CSV file) from the prior sensor wear. Additionally, CGM reports and pump reports will be downloaded from 30 days before V14 to V14 and from V13 to V14 using Carelink for Medtronic CGM and pumps, CGM reports/data and pump reports/data will be downloaded from 30 days before V14 to V14 and from V13 to V14 using Clarity for Dexcom CGM and t:connect for Tandem pumps (

Confidential Page 26 of 70

). The site will de-identify all reports and data. Basal insulin dosages will be documented. See Section 3.7 for information on the assessments to be performed at these visits.

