**Table 3: Schedule of Assessments** 

| Study Period  | Screen                      | Treatment Period |    |    |    |    |    |    |    |      |                 |      |     |             |      |
|---|-----------------------------|------------------|----|----|----|----|----|----|----|------|-----------------|------|-----|-------------|------|
| In-clinic Visit (V) Telehealth Visit (T)                  | V1                          | V2               | Т3 | T4 | T5 | T6 | T7 | T8 | V9 | T10  | T11             | T12  | V13 | V14         | ET c |
| Day   | Up to
28 Days            | 0                | 1  | 2  | 4  | 7  | 14 | 21 | 30 | 37 b | 44 b | 51 b | 80  | 90
(EOT) |      |
| Visit Window (Days)                                       | Before Random. a |                  |    |    |    | ±2 | ±2 | ±2 | +7 | ±2   | ±2              | ±2   | +2  | +7          |      |
| Informed consent  | X                           |                  |    |    |    |    |    |    |    |      |                 |      |     |             |      |
| Eligibility criteria confirmed                            | X                           | X                |    |    |    |    |    |    |    |      |                 |      |     |             |      |
| Demographics and medical history                          | X                           |                  |    |    |    |    |    |    |    |      |                 |      |     |             |      |
| Randomization   |                             | X                |    |    |    |    |    |    |    |      |                 |      |     |             |      |
| Physical examination, including weight and height         | X                           |                  |    |    |    |    |    |    |    |      |                 |      |     | X           | X    |
| Prior/concomitant medications                             | X                           | X                | X  | X  | X  | X  | X  | X  | X  | X    | X               | X    | X   | X           | X    |
| Smoking status and evaluation of pulmonary toxin exposure | X                           |                  |    |    |    |    |    |    |    |      |                 |      |     | X           | X    |
| Adverse events d  | X                           | X                | X  | X  | X  | X  | X  | X  | X  | X    | X               | X    | X   | X           | X    |

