| Dispense insulin
degludec and injection
supplies, as necessary
(Afrezza + Insulin
Degludec group only) |                             | X  |                  |    |    |    |    |    | X  |      |                 |      |     |             |      |
| Record basal insulin
dosages (Afrezza +
Insulin Degludec
group only)                                      |                             | X  |                  |    |    |    |    |    | X  |      |                 |      | X   | X           |      |
| Collect Afrezza unused inhalers and cartridges as well as any unopened bottles of insulin degludec                 |                             |    |                  |    |    |    |    |    |    |      |                 |      |     | X           | X    |

Page 39 of 70

AID=automated insulin delivery, CGM=continuous glucose monitoring, COVID-19=coronavirus 2019, EOT=end of treatment, ET=early termination, FEV1=forced expiratory volume in 1 second, HbA1c=glycated hemoglobin A1c, RAA=rapid-acting insulin analog, Random=randomization, Screen=screening, SMBG=self-monitored blood glucose, TSH=thyroid-stimulating hormone.

- a. The Screening Visit should be scheduled 10 days (+ 4 days) before the subject's expected date of randomization. When subjects return for Visit 2, blinded CGM data will be downloaded and CGM sensor wear evaluated. If CGM sensor wear time is inadequate, per the discretion of the Investigator, the Screening Period can be extended (this becomes an unscheduled visit) and sensor wear can be repeated once. The subject will return to the clinic 10 days (+ 4 days) later and, if sensor wear is adequate and all eligibility criteria met, be randomized to study treatment and proceed with the meal challenge and Visit 2 assessments. Visit 2 should be within 4 days of the end of the final sensor wear data (i.e., the CGM sensor with adequate wear time).
- b. The timing of telephone visits T10, T11, and T12 is relative to Visit 9 (T10 should occur 7 days [±2 days] from Visit 9, T11 is 14 days [±2 days] from Visit 9, and T12 is 31 days [±2 days] from Visit 9).
- c. A sample should be collected for HbA1c at the ET visit if the subject discontinues the study after 4 weeks of participation.
- d. Any adverse event that occurs after the subject enrolls in the study (consent date) will be recorded.

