- e. Subjects will be asked to provide a recent negative COVID-19 test (if available), confirm they have no symptoms of COVID-19, or provide evidence of COVID-19 vaccination.
- f. Subjects should use their study provided blood glucose meter to take an SMBG value if their CGM reading is <70 mg/dL or if their CGM reading does not match their symptoms or expectations. Hypoglycemic episodes will be defined as all SMBG measurements <70 mg/dL. See Section 3.9.2.6.
- g. A negative urine pregnancy test is required for enrollment, from all female subjects of child-bearing potential. After enrollment, additional pregnancy tests may be conducted as needed at the discretion of the Investigator.
- h. A documented normal level within 6 months of screening can be used in lieu of testing.
- i. CGM reports and pump reports will be downloaded from V1 to V2 at V2, V2 to V9 and 10 days before V9 to V9 at V9, V9 to 30 days after V9 at V13, and 30 days before V14 to V14 and V13 to V14 at V14 using Carelink for Medtronic CGM and pumps. CGM reports/data and pump reports/data will be downloaded from V1 to V2 at V2, V2 to V9 and 10 days before V9 to V9 at V9, V9 to 30 days after V9 at V13, and 30 days before V14 to V14 and V13 to V14 at V14 using Clarity for Dexcom CGM and t:connect for Tandem pumps. The site will de-identify all reports and data.
- j. Subjects in the Afrezza + AID group will be instructed not to enter carb intake/meal announcements in the pump system. In the event that they accidentally enter carb intake/meal announcement for a certain meal, they should NOT dose Afrezza for that same meal. If they accidentally take Afrezza with a meal announcement, carbs or glucagon should be administered. For subjects in the Afrezza + AID group, the site will confirm at every visit (phone or in person) to make sure they are not entering carb intake/meal announcements in the pump system.
- k. Only applies to subjects in the Afrezza + Insulin Degludec group who use a Medtronic 670G/770G system.

Confidential Page 40 of 70

Table 4: CGM/Pump Reports and Data to be Downloaded

| Reports/Data to be Downloaded                 | V2 | V9 | V13 | V14 |
|---|----|----|-----|-----|
| Blinded G6 PRO Data                           | X  |    |     | X   |
| V1 to V2 CGM/pump report/data                 | X  |    |     |     |
| V2 to V9 CGM/pump report/data                 |    | X  |     |     |
| V9 minus 10 Days to V9 CGM/pump report/data   |    | X  |     |     |

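### V13, which places the end-of-treatment blinded CGM sensor, has three different timings; when V14 falls on Day 93–97, no V13 day meets both Table 3 and Section 3.1

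*Protocol*

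**What the plan says.** The protocol times V13 in three ways (V2 is Day 0).

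- **Section 3.7.6** (the V13 procedures): "This visit will be conducted at least 30 days (+7 days) after Visit 2". With its window this is Day 30–37. The same sentence describes V9 in the synopsis and Section 3.1.
- **Table 3**: Day 80 with a window of +2, so Day 80–82.
- **Synopsis and Section 3.1**: "This visit will occur 8 to 10 days prior to Visit 14".

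For V14, Section 3.1 says: "At least 90 days following Visit 2 (+ 7 days), subjects will return for HbA1c measurement". Table 3 agrees (Day 90, +7), so V14 may fall on Day 90–97.

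V13 is where the second blinded Dexcom G6 Pro sensor is placed on all subjects. Sections 1.3.3 and 3.9.1.1 say that this wear covers the final 10 days of the study. SAP Section 8.1 bases the secondary CGM metrics (TIR, TBR, time <54 mg/dL, TAR, time >250 mg/dL, CV) on the G6 Pro data.

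**The concern.** A site cannot follow all three statements, and for late V14 visits it cannot follow even the two workable ones. V13 places the only blinded sensor worn after baseline, so its date decides which days the end-of-treatment CGM values describe. If V13 stays at Day 80–82 while V14 moves to Day 93–97, the recording can stop before V14 and miss part of the final 10 days. If V13 moves with V14, it falls outside the Table 3 window.

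The second consequence concerns deviations. SAP Section 8.2.2 allows endpoint data from outside the visit window to be treated as missing in the per-protocol population. With conflicting windows for V13, it is unclear which recordings that rule reaches. The planned groups are 10, 10 and 5 subjects, so each recording counts, even in a descriptive summary.

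**Working it through.** **Step 1. Can the Section 3.7.6 timing be meant?** V9 is on Day 30–37. Three things due at or before V13 fall later:

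- The download due at V13 (Table 3 footnote i) is "V9 to 30 days after V9 at V13". It is complete only on Day 30 + 30 = 60 to 37 + 30 = 67.
- T12 precedes V13. Table 3 shows it at Day 51, which is V9 + 21 for V9 on Day 30. With ±2 days and V9 on Day 30–37 this gives Day 49–60. Section 3.7.5 says "T12 is 31 days (±2 days) from Visit 9", and Table 3 footnote b agrees; that gives Day 59–70. Both are after Day 37.
- Section 3.7.6 itself lists "Instruct participants to log meal announcements and Afrezza doses in the final 10 days". V13 on Day 30–37 would be 90 − 37 = 53 to 97 − 30 = 67 days before V14.

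The Day 30–37 timing is therefore a copying error from V9.

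**Step 2. Reproduce Table 3 from Section 3.1.** For V14 on Day 90, the 8-to-10-day rule gives V13 on Day 90 − 10 = 80 to 90 − 8 = 82. This is exactly Table 3's Day 80 (+2).

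**Step 3. Let V14 move through its window.** For each V14 day, Section 3.1 requires V13 in [V14 − 10, V14 − 8], and Table 3 requires [80, 82]. The last two columns assume that the site follows Table 3 and that the sensor is worn for 10 days. Then lag = max(0, gap − 10). Days covered out of the last 10 equal the gap when it is 10 or less, and 10 + 10 − gap when it is larger.

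| V14 day | V13 by Section 3.1 | V13 days meeting both | Gap under Table 3 (days) | Lag, sensor end to V14 (days) | Days covered of last 10 |
|---|---|---|---|---|---|
| 90 | 80–82 | 80, 81, 82 | 8–10 | 0 | 8–10 |
| 91 | 81–83 | 81, 82 | 9–11 | 0–1 | 9–10 |
| 92 | 82–84 | 82 | 10–12 | 0–2 | 8–10 |
| 93 | 83–85 | none | 11–13 | 1–3 | 7–9 |
| 94 | 84–86 | none | 12–14 | 2–4 | 6–8 |
| 95 | 85–87 | none | 13–15 | 3–5 | 5–7 |
| 96 | 86–88 | none | 14–16 | 4–6 | 4–6 |
| 97 | 87–89 | none | 15–17 | 5–7 | 3–5 |

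Table 3 permits 3 × 8 = 24 pairs of V13 and V14 dates. Of these, 3 + 2 + 1 = 6 meet the 8-to-10-day rule and 18 do not. Of the 18, 5 × 3 = 15 have V14 on Day 93–97, where no choice of V13 meets both rules. These are counts of permitted dates, not probabilities.

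**Step 4. Vary the wear time.** The documents do not state the sensor's wear time. Ten days is inferred from Section 3.9.1.1, which allows as much as 20 days at baseline for one wear and one repeat. As a shorter assumption, take 8 days, the shortest Section 3.1 interval. For V14 on Day 93–97 under Table 3:

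- Lag: 11 − 8 = 3 to 17 − 8 = 9 days.
- Days covered of the last 10: 8 + 10 − 17 = 1 to 8 + 10 − 11 = 7.

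**Step 5. Compare with Section 3.1.** With a gap of 8, 9 or 10 days and 10 days of wear, the lag is 0 and 8, 9 or 10 of the last 10 days are covered, whatever the V14 day.

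**The case against.** The strongest reply is that the sentence in Section 3.7.6 is an obvious slip and that the other two rules agree at the nominal V14 on Day 90. A site that books V14 for Day 90–92 can meet both. On this view the only real gap is that Table 3's V13 window does not move when V14 is late. That is a fair description, but Day 93–97 is 5 of the 8 permitted V14 days, and on those days a site must break one instruction. Section 3.7 refers to Table 3 for which procedures occur at which visits. It does not say which timing prevails.

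The 18 of 24 count includes 3 pairs in which another V13 day would have met both rules. The unavoidable conflict is the 15 pairs with V14 on Day 93–97. The 8-day case also rests on a visit interval, not a known sensor life, so the 10-day figures are the better supported.

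The protocol accepts some lag at baseline: Table 3 footnote a and Section 3.7.2 ask for V2 within 4 days of the end of sensor wear. With 10 days of wear, 3 + 3 + 2 + 1 + 0 = 9 of the 15 late pairs have a lag of 4 days or less. The other 6 exceed it, and no such limit is set at end of treatment.

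Finally, the consequence is modest, and this stands. The CGM metrics are secondary and descriptive. The rule on out-of-window data applies to the per-protocol population, while ITT is the primary efficacy population. The last scheduled titration is at V13, and unblinded CGM from V13 to V14 is also downloaded.

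**Conclusion.** The concern holds. The Section 3.7.6 timing is wrong as written, and Table 3 and Section 3.1 cannot both be followed when V14 is on Day 93–97: Section 3.1 then needs V13 on Day 83–89, and Table 3 allows only Day 80–82. The date arithmetic is exact. The loss of coverage under Table 3, with the blinded data ending 1–7 days before V14, depends on the assumed 10 days of wear. The documents do not show how often V14 will fall that late.

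The effect is confined to the coverage of the secondary CGM metrics and to the classification of window deviations. HbA1c is measured at V14 and is unaffected. No bias in the CGM metrics has been shown. The correction should be made because these are operative instructions for the visit that supplies the end-of-treatment G6 Pro data, and the change is small.

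**What to change.** Reconcile the passages to one V13 window:

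1. Delete the Day 30–37 sentence from Section 3.7.6.
2. In Table 3, replace Day 80 (+2) with V13 timed relative to the scheduled V14 date, using the rule already in the synopsis and Section 3.1 (8 to 10 days before V14).
3. Optionally, cite that window in SAP Section 8.2.2, so that the rule on out-of-window data has a defined reference.

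The two T12 timings (Day 51 in the Table 3 column; V9 + 31 in footnote b and Section 3.7.5) also need to be reconciled. They do not affect the result above.

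The cost is one sentence and one table cell, with no extra visit or sensor. Sites must book V13 and V14 together. Two weaknesses remain. If V14 slips after the sensor is placed, a lag can still occur: with V14 booked for Day 90, the sensor placed on Day 80–82 and V14 held on Day 97, the gap is 15–17 days and the lag 5–7 days at 10 days of wear. An 8-day interval also covers only 8 of the last 10 days.

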## 3.7.7 Visit 14 / Early-Termination Visit

The following procedures will be performed at Visit 14, or if the subject discontinues early, at the early-termination visit:

Perform all safety assessments

Download and de-identify data from Dexcom G6 Pro device (

Confidential Page 50 of 70

• )

mannkind

Download and de-identify of unblinded CGM reports and pump reports for Medtronic CGM and pumps (

Confidential Page 51 of 70

mannkind

Download and de-identify of unblinded CGM reports/data and pump reports/data for Dexcom CGM and t:connect for Tandem pumps (

Confidential Page 52 of 70

- )
- Collect meal announcements and Afrezza dose log for final 10 days
- Collect blood for laboratory tests (see Section 3.9.2.8)
- Record concomitant medications
- Record current basal insulin dosages
- Measure and record FEV1
- Record AEs

### 3.8 Post Study Interview

An optional post-study interview may be conducted for those subjects who opt-in to participate, as indicated in the Informed Consent Form. The goals of the post-study interview are to gain insight into the subject's experience living with diabetes, their experience in the study (both positive and negative), and learn about how being in the study has affected their quality of life.

Sites will share the subject's contact information with the interviewer once the subject has opted in to participate. Responses to the questions will be summarized and shared with the Sponsor.

### 3.9 Procedures for Subjects Who Prematurely Withdraw from the Study

Any subject who discontinues treatment prematurely should have an early-termination visit conducted as soon as possible to complete the assessments indicated in Table 3.

### 3.9.1 Efficacy Assessments

### 3.9.1.1 Continuous Glucose Monitoring

Subjects will wear a blinded CGM at baseline for up to 20 days during an up to 28-day screening period and during the last 10 days of the study. Additionally, subjects will measure their glucose throughout the study using an unblinded CGM system (sensors, transmitter). Subjects will be instructed at Visit 2 in the operation of their CGM device.

### 3.9.1.2 Self-Monitored Blood Glucose

Confirmatory blood glucose values for CGM readings <70 mg/dL should be self-measured by the subject using a study-provided blood glucose meter and corresponding supplies (lancets, test strips, etc.). Subjects will also be instructed to use their blood glucose meter to take an SMBG value if they suspect DKA accompanied by a CGM value >250 mg/dL, or if their CGM reading does not match their symptoms or expectations, to make treatment decisions.

### 3.9.2 Safety Assessments

## 3.9.2.1 Medical History and Demographics

A detailed medical history should be taken to assess whether or not subjects meet the inclusion/exclusion criteria, including history of diabetes (i.e., date of clinical diagnosis of T1DM, start date of current insulin treatments and treatment name). In addition, subjects will be

Confidential Page 53 of 70

queried about drug and environmental allergies, family pulmonary disease history, and their smoking status.

Demographic data, including age (years), race, ethnicity, and gender (male, female, other, or "decline to state") will also be collected.

### 3.9.2.2 Physical Examinations

A physical examination, including general appearance, ear, nose, throat, lung, and cardiac auscultation will be performed at Visit 1.

Abbreviated physical examinations will be performed as deemed appropriate by the Investigator for safety reasons; these abbreviated physical examinations will include, but are not limited to, general appearance, vital signs, mental status, respiratory and cardiovascular systems, and other evaluations, as needed.

All changes identified as clinically noteworthy must be recorded in an AE page of the CRF.

